7.1.2 Disease Parameters

Measurable disease: Measurable lesions are defined as those that can be accurately measured in at least one dimension (longest diameter to be recorded) as ≥ 20 mm with conventional techniques (CT, MRI, x-ray) or as ≥ 10 mm with spiral CT scan. All tumor measurements must be recorded in millimeters (or decimal fractions of centimeters).

Note: Previously irradiated lesions are non-measurable except in cases of documented progression of the lesion since the completion of radiation therapy.

Non-measurable disease: Will be evaluated clinically. The response will be recorded based on the clinical digital exam.

Target lesion: For purposes of this study the cervical tumor is the target lesion, longest diameter (LD) will be measured from T2W MR study if available or contrast CT scan. The baseline LD will be used as reference by which to characterize the objective tumor response.

Non-target lesions: All other lesions (or sites of disease) including any measurable lesions over and above the 6 target lesions should be identified as **non-target lesions** and should also be recorded at baseline. Measurements of these lesions are not required, but the presence or absence of each should be noted throughout follow-up.

7.1.3 Methods for Evaluation of Measurable Disease

All measurements should be taken and recorded in metric notation using a ruler or calipers. All baseline evaluations should be performed as closely as possible to the beginning of treatment and never more than 28 days before the beginning of the radiation treatment.

The same method of assessment and the same technique should be used to characterize the identified and reported lesion at baseline and during follow-up. Imaging-based evaluation is preferred to evaluation by clinical examination when both methods have been used to assess the antitumor effect of a treatment.

Conventional CT or MRI: These techniques should be performed with cuts of 5 mm or less in slice thickness contiguously. Spiral CT should be performed using a 5 mm contiguous reconstruction algorithm. This applies to tumors of the chest, abdomen, and pelvis. Study Patients should receive some form of cross sectional imaging before initiation of therapy as well as at least once within fourteen months after completion of therapy.

7.1.4 Response Criteria

7.1.4.1 Evaluation of Target Lesions

Complete Response (CR): Disappearance of target lesions, determined by two separate observations conducted not less than 4 weeks apart. There can be no appearance of new lesions.

Partial Response (PR): At least a 30% decrease in the of the longest diameter (LD) of target lesions, taking as reference the baseline sum LD. There can be no appearance of new lesions.

Progressive Disease (PD): At least a 20% increase in the LD of target lesions, taking as reference the smallest sum LD recorded since the treatment started, or the appearance of one or more new lesions.

Stable Disease (SD): Neither sufficient shrinkage to qualify for PR nor sufficient increase to qualify for PD, taking as reference the smallest sum LD since the treatment started.

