7.0 MEASUREMENT OF EFFECT

7.1 Antitumor Effect

Response and progression will be evaluated in this study using the new international criteria proposed by the Response Evaluation Criteria in Solid Tumors (RECIST) Committee [*JNCI* 92(3):205-216, 2000]. Changes in only the largest diameter (unidimensional measurement) of the tumor lesions are used in the RECIST v1.1 criteria.

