7.1.6 Progression-Free Survival

Progression-free survival (PFS) is defined as the duration of time from start of treatment to time of progression.

This will be further differentiated as Local tumor (cervix-which is primary endpoint) , Regional(pelvic nodal) and distant (Paraortic and visceral organ)metastases.

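### Progression of the cervical target is a 20% rise over the smallest diameter with no absolute minimum, so reading error in a small residual read twice can produce a false local event

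*Combined protocol and SAP*

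**What the plan says.** Section 7.1.4.1 (Evaluation of Target Lesions) sets progression at "At least a 20% increase in the LD of target lesions, taking as reference the smallest sum LD" on record from the start of treatment, or new lesions. It states no absolute minimum and no confirmation of progression, although complete response needs a second observation at least four weeks later.

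Section 7.1.2 (Disease Parameters) names a single target: "For purposes of this study the cervical tumor is the target lesion". Its longest diameter (LD) is read from T2-weighted MR if available, otherwise contrast CT. Lesions are measurable "as ≥ 20 mm with conventional techniques (CT, MRI, x-ray") "or as ≥ 10 mm with spiral CT scan". A note in the same section classes previously irradiated lesions as non-measurable unless progression has been documented, and sends non-measurable disease to digital examination.

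Section 7.1.3 asks for "cuts of 5 mm or less in slice thickness contiguously" and prefers imaging to examination when both have been used.

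Section 7.1.6 divides progression by site, the first being "Local tumor (cervix-which is primary endpoint"). Section 7.1 cites the 2000 RECIST publication, then says that changes in the largest diameter of "tumor lesions are used in the RECIST v1.1 criteria".

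Only one post-treatment scan is required, within fourteen months (Sections 6.3.1, 6.4 and 7.1.3). More are allowed.

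**The concern.** A purely relative threshold shrinks with the lesion. With one target there is no sum over several lesions to average out reading error, and the reference is the smallest value seen, which an unusually low reading pulls down. Once the residual is small, the change that counts as progression is a few millimetres, and a repeat reading of an unchanged lesion may cross it.

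Local progression is the primary endpoint and few true events are expected, so a false one is costly. It would be counted against the 85% target and could hide a real improvement over 65%.

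**Working it through.** **1. The plan's own figure.** Inputs from Section 8.3.1: 2-year rates of 65% and 85%, two-sided α 0.10, 80% power, 2 years' accrual plus 2 years' follow-up, exponential times, no loss.
- Hazard λ = −ln(S)/2: λ0 = 0.2154, λ1 = 0.0813 per year; ratio 0.377.
- Event probability P = 1 − (e^(−2λ) − e^(−4λ))/(2λ): P0 = 0.472, P1 = 0.215.
- Expected events in 21 patients: 9.9 under the null, 4.5 under the alternative.
- Log-hazard method: n = [(1.645/√P0 + 0.842/√P1)/ln(λ0/λ1)]² = 18.6.
- Cube-root method: n = [(1.645·λ0^(1/3)/(3√P0) + 0.842·λ1^(1/3)/(3√P1))/(λ0^(1/3) − λ1^(1/3))]² = 19.8.
- One-sample log-rank: with e = P1·λ0/λ1 = 0.571, n = [(1.645√e + 0.842√P1)/(e − P1)]² = 21.1.

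The planned 21 is therefore reproduced to within about two patients. Simulated power at n = 21 is 0.77 (log-rank, variance E) to 0.84 (variance (O+E)/2, or cube-root).

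**2. The trigger in millimetres.** 0.20 × LD is 2, 3, 4 and 5 mm at a smallest LD of 10, 15, 20 and 25 mm. It is below 5 mm for any smallest LD under 25 mm.

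**3. Unchanged lesion, two readings.** Assume independent normal reading errors with SD s of 1, 2 or 3 mm. The second reading is at least 1.2 times the first with probability 1 − Φ(0.2·LD/(s√2.44)), because 1 + 1.2² = 2.44. With a floor the rise must also reach 5 mm. Below 25 mm the floor is almost always the binding condition, and the probability is close to 1 − Φ(5/(s√2)).

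| LD | Rule | s = 1 | s = 2 | s = 3 |
|---|---|---|---|---|
| 10 mm | 20% only | 10.0% | 26.1% | 33.5% |
| 20 mm | 20% only | 0.5% | 10.0% | 19.7% |
| 10 or 20 mm | 20% and 5 mm | 0.02% | 3.9% | 11.9% |

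Simulation of repeat readings agrees.

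**4. Shrinking lesion, one scan before and one after.** With true diameters a before and b after, the probability is 1 − Φ((1.2a − b)/(s√2.44)).
- 40 to 10 mm: 0% at every s.
- 20 to 14 mm: 0%, 0.07%, 1.6%.
- 15 to 10 mm: 0%, 0.5%, 4.4%.

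The rates in step 3 therefore need a residual that is already small and static before the boost, or at least two post-treatment scans.

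**5. What a false event would cost.** This is a scenario, not an estimate. Under the 85% alternative, give each patient a 1/21 (4.8%) chance of a false event at a random time from 3 to 24 months. Power falls from 0.77–0.84 to 0.62–0.71. At 2/21 (9.5%) it falls to 0.47–0.57.

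**The case against.** Much of the case on the other side stands.

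- **Schedule.** One post-treatment scan is required, and the usual course is shrinkage from a larger lesion. Step 4 then gives a small risk. Simulating three readings of an unchanged 10 mm lesion gives 23–63%, and a reader might take that as this trial's rate. The protocol does not require the imaging that figure needs.
- **Scoring as local failure.** A reader might infer that the protocol declares every such 2–4 mm change a local failure. It does not say so outright. The link is inferred from Sections 7.1, 7.1.4.1 and 7.1.6. Local failure has no definition of its own, and Section 8.5.1 bases the reported control rate on imaging together with examination.
- **Irradiated lesions.** The note in Section 7.1.2 could take the irradiated residual out of diameter measurement altogether, and a 10 mm residual on MR is below the 20 mm limit given there. But the same section names the cervical tumor as the target measured by LD. The conflict does not remove the problem; it leaves the governing rule unsettled.
- **Slice thickness.** A reader might infer that changes under 5 mm cannot be resolved. Slice thickness mainly limits the cranio-caudal direction and is not the error of an in-plane diameter. Here 5 mm is only a convenient benchmark for a floor.
- **RECIST version.** Whether naming v1.1 brings in a further condition cannot be settled from these documents. The rule actually written out has none.
- **Partial remedy.** With s = 3 mm, about 12% remains after the floor, and the floor is not a confirmation step.

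**Conclusion.** The point holds in a conditional form. Followed as written, Section 7.1.4.1 lets a 2–4 mm change in a 10–20 mm residual count as progression of the only target lesion, and Section 7.1.6 carries local progression into the primary endpoint. When such a residual is read at least twice without true change, the chance of a false event is about 10–33% at 10 mm and 0.5–20% at 20 mm, against about 0–12% with a 5 mm floor. When a shrinking lesion has only the one required scan, it is about 0–4%. All of these rest on the assumed reading SD of 1–3 mm and on independent errors.

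A reader might infer that one or two of the 21 patients will be false failures. The documents do not support any count: they give no residual sizes, no share of patients with a persistent small lesion and no number of extra scans. What they do support is that about 4.5 true events are expected at 85% control, so a single false one would matter. The error lowers power and biases against the treatment; it would not produce a false claim of benefit. The planned sample size of 21 is unaffected.

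**What to change.** - **Section 7.1.4.1:** for diameter-based progression of the cervical target, require both a 20% increase and an absolute increase of at least 5 mm over the smallest LD. Unequivocal regrowth on examination, or on biopsy where done, should still count.
- **Section 7.1.6:** state that this is the local-failure event for the primary analysis.
- **Section 7.1.2:** reconcile the note on irradiated, non-measurable lesions with the choice of the irradiated cervix as the measured target.
- **Section 7.1:** name and cite one RECIST version that matches the written rule.

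The cost is a few sentences and a corrected citation, with no change to the sample size. The one small downside is that slow true regrowth of a small residual may be dated one assessment later. The change concerns how the endpoint is scored, not how patients are managed.

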1. BACKGROUND AND RATIONALE

1.1 Disease Background

Locally Advanced Cervical Cancer (LACC)

There will be an estimated 12,300 new cases of cervical cancer diagnosed in the United States in 2013, with one third that number dying from the cancer [1]. While the incidence of cervical cancer in the United States has been gradually declining as a result of widespread screening, outcomes still remain poor for many with cervical cancer. In addition there has been a negligible survival improvement over the past decade. [2] Even with the increased screening in the U.S., 48% of patients still present at an advanced stage [2]. Globally cervical cancer is widespread (no. 3 cancer in women) and lethal (with a mortality incidence ratio of 52%) [3]. Several prospective randomized trials compared concurrent chemotherapy and radiation to radiation alone for advanced cervical cancer and showed substantial improvement in local control and overall survival in the late nineties [4, 5]. As a result, the National Cancer Institute issued a treatment alert in 1999 establishing chemoradiation as the standard of care for advanced cervical cancer. Radiotherapy for cervical cancer currently consists of radiation in the form of external beam delivered over 5-6 weeks of daily therapy followed by or interdigitated with intracavitary or less frequently, interstitial brachytherapy. These procedures remain invasive and require use of supportive medications ranging from general anesthesia in the operating room to a combination of sedatives and narcotics for insertion of the brachytherapy devices. Furthermore, intracavitary brachytherapy delivers dose to a limited volume of tissue around the cervix and may be inadequate for delivering dose to tumors that extend to the pelvic sidewall. As a result, even with the use of chemoradiation, approximately 30% of patients with locally advanced disease will have a locoregional recurrence [5]. These results of best local control for Stage III-IVA cervix cancer of 70% applies to carefully chosen patients in clinical trials. Patients with bulky advanced cervical cancers like the vast majority of patients we see at Parkland (PMH) and UTSW have an inferior local control which is hampered by poor performance status of these patients. In a recent review of patients from 2003-2011 at PMH, the actuarial overall survival for all II-IVa pts was only 34% at 5 years [6]. A significant group of patients had locoregional failure or persistence, presumably due to bulky tumor volume exceeding the limitations of available radiation and chemotherapeutic modalities. Additionally, patients often present with multiple untreated co-morbidities which makes them often unable to undergo standard chemoradiation and brachytherapy often compromising the delivery of adequate radiation dose and hence the tumor local control. Furthermore, current treatments are often unpalatable for many patients because they are either too invasive, inconvenient or inadequate.

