3.1 Inclusion criteria

- 3.1.1 Biopsy proven Locally Advanced stage Cervical Cancer (LACC, FIGO IB2 – IVB)
- 3.1.2 Zubrod performance status 0-3
- 3.1.3 Women of child-bearing potential (See note) must agree to use adequate contraception (hormonal or barrier method of birth control; abstinence) prior to study entry and for the duration of study treatment. Should a woman become pregnant or suspect she is pregnant while participating in this study, she should inform her treating physician immediately.
- 3.1.4 Patients should have **any of** the below to be eligible
- Are not candidates for intracavitary brachytherapy due to poor geometry or poor response to external beam RT
 - Patients with co-morbid medical conditions, bleeding disorders, poor anesthetic risk precluding brachytherapy
 - Patients who refuse brachytherapy or prefer external beam hypofractionated approach
 - Patients requiring interstitial brachytherapy

Note: Patients may be discovered during standard therapy and enrolled prior to boost.

Note: A female of child-bearing potential is any woman (regardless of sexual orientation, having undergone a tubal ligation, or remaining celibate by choice) who meets the following criteria:

- Has not undergone a hysterectomy or bilateral oophorectomy; or
- Has not been naturally postmenopausal for at least 12 consecutive months (i.e., has had menses at any time in the preceding 12 consecutive months).

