8.3 Sample Size

8.3.1 Overview

Six patients will be used for a safety lead-in stage in this phase II clinical trial. In Standard Phase 1 3+3 clinical trials, there is 0 or 1 DLT out of 6 patients at the MTD, which will be used for a subsequent phase II clinical trials. [36] Prior studies have shown the rate of \geq grade 3 GI toxicity to be 7-14% and 2-5% for \geq grade 3 GU toxicity. The treatment will not be considered to be feasible if the rate of acute GI/GU toxicity is $>30\%$. In this phase II clinical trial, six patients will be used in a safety lead-in stage. If there is 0 or 1 DLT out of 6 patients at the safety lead-in stage, we will proceed to a phase II clinical trial. Otherwise, we will stop the trial, and will not proceed to a phase II trial with a given dose.

The primary goal of this study is to assess the 2 year pelvic local control (excluding nodes) from cervix cancer. Historical data shows that the 2 yr-pelvic local control rate is approximately 65%. [4, 5, 9] We expect that this will be increased to 85% with the treatment of cervix Image Guided Hypofractionated Radiation Treatment boost based on best results with Intracavitary/interstitial data [13]. We assume that the loco regional recurrence-free survival follows an exponential distribution. Accrual to the study is assumed to be uniformly distributed over time with no loss to follow-up. Twenty-one patients will achieve 80% power in detecting the difference between the null hypothesis of 2-year recurrence-free survival rate of 65% and the alternative hypothesis of 2-year recurrence-free survival rate of 85% at a two-sided 0.1 significance level assuming a 2-year accrual period and 2-year follow-up period. It is expected that 21 patients will be recruited in 2 years with an expected accrual rate of 10-11 patients per year.

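### Section 8 leaves local failure undefined, and the only operational rule (RECIST progression) counts persistent, non-growing cervical tumor as local control

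*Combined protocol and SAP*

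**What the plan says.** Section 8 gives the primary outcome several names: local control, pelvic local control excluding nodes, recurrence-free survival, time to local failure, and local recurrence-free survival. It does not say what event ends any of them. Section 8.5.1 says that pelvic control is based on imaging and examination, without a criterion for failure.

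The operational content is in section 7. Section 7.1 says that progression is judged by RECIST. Section 7.1.6 runs the time from start of treatment to progression and then says "This will be further differentiated as Local tumor (cervix-which is primary endpoint". Section 7.1.4.1 defines target-lesion progression as "At least a 20% increase in the LD of target lesions, taking as reference the smallest sum LD recorded since the treatment started"; new lesions also qualify. Section 7.1.2 names the cervical tumor as the target lesion. Anything between a 30% shrinkage and progression is stable disease.

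Two other places bear on persistence. Section 1.1 reports of the institution's own 2003-2011 patients that "A significant group of patients had locoregional failure or persistence". Section 3.1 lists "poor response to external beam RT" among the routes into the trial.

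The design is in section 8.3.1: "Twenty-one patients will achieve 80% power in detecting the difference" between 2-year rates of 65% and 85%, "at a two-sided 0.1 significance level assuming a 2-year accrual period and 2-year follow-up period", with exponential times and no loss to follow-up. Section 8.5.1 names a one-sample log-rank test against 65%.

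**The concern.** After definitive radiotherapy, a cervical tumor that never clears would commonly be regarded as a local failure, and section 1.1 itself names persistence alongside failure. Under the section 7 rule such a tumor generates no event unless it grows 20% from its smallest size. The patient is censored in the Kaplan-Meier estimate and the log-rank test, and so contributes to control at 2 years. Eligibility admits patients who responded poorly to external beam treatment, a group in whom residual tumor is plausible.

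A single-arm test against a fixed historical rate is valid only if the trial and the historical figure count the same events. If the 65% treated persistence as failure and the trial does not, the trial could be declared a success partly because residual tumor is scored as controlled.

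**Working it through.** **Inputs from section 8.3.1.** n = 21; null 65% and alternative 85% at 2 years; two-sided alpha 0.10 (1.645 per tail); 2 years' uniform accrual plus 2 years' follow-up; exponential times; no dropout.

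**Reproducing the plan's figure.**
- Hazards: -ln(0.65)/2 = 0.2154 and -ln(0.85)/2 = 0.0813 per year.
- Observed events per patient under the alternative: O = 1 - [exp(-2h) - exp(-4h)]/(2h) with h = 0.0813, which gives 0.2155.
- Expected events per patient under the null hazard, over the same exposure: E = 0.2154 × 0.2155/0.0813 = 0.571.
- n = [(1.645√E + 0.842√O)/(E - O)]² = [(1.243 + 0.391)/0.356]² ≈ 21.1. Power at n = 21 is 0.798.

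The stated 21 patients and 80% power are reproduced. Simulated power at 85% is about 77%. The simulated chance of declaring improvement at a true 65% is about 3.6%, against a nominal 5% per tail.

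**Weight of one patient.** 1/21 = 4.8 percentage points on the crude rate. The planned difference is 85 - 65 = 20 points.

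**Effect on the test.** Two inputs are assumed because the documents do not give them.
- The historical 65% counts persistence as failure.
- The share q with persistent tumor is 5%, 10% or 15%.

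True 2-year control with persistence counted as failure is held at 65%, so the other patients have (1 - q)S(2) = 0.65. The trial counts growth only. If persistent tumor never grows, the apparent 2-year rate is 65% + q, that is 70%, 75% or 80%.

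The table gives the chance of declaring success (one-sample log-rank, z < -1.645, n = 21, at least 100,000 simulated trials per cell). Without persistent tumor it is about 4%.

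| Course of residual tumor (assumed) | q = 5% | q = 10% | q = 15% |
|---|---|---|---|
| Progresses after 6 months, median 1 further year | 6% | 9% | 13% |
| Progresses after 6 months, median 2 further years | 7% | 13% | 22% |
| Never grows (worst case) | 11% | 27% | 52% |
| Persistence counted as failure at 6 months | 4.5% | 5.5% | 6.8% |

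**The reverse case.** Suppose that 85% is a progression-only rate. Control with persistence counted as failure is then 85% - q = 80%, 75% or 70%. Power against 65% falls from about 77-80% to about 50%, 25% and 11%.

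**The case against.** Four objections deserve an answer.

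- **The RECIST rule is an inference.** Section 8 never adopts it. It follows from joining sections 7.1, 7.1.4.1 and 7.1.6. Section 7.1.2 also calls previously irradiated lesions non-measurable unless they have progressed, and sends non-measurable disease to clinical examination, so the 20% rule may not apply cleanly to a cervix that has had 45 Gy. This stands as a limit on wording. It does not remove the gap, because neither section 7.1.2 nor section 8.5.1 makes persistence a failure, and section 7.1.6 ties the primary endpoint to progression.
- **The comparator may be recurrence-based.** A reader might infer that the trial's rate is certainly inflated against 65%. The documents do not support that. Section 8.3.1 does not say how the 65% was counted. For two of the sources cited for it, section 1.1 speaks of recurrence (about 30% locoregional in one, 25% local in the other). The remark about persistence concerns the institution's own review, which is not cited for the 65%. This objection stands: the bias in the test is conditional.
- **Residual tumor can progress later.** A reader might take 52% as the trial's false-positive rate. It requires 15% persistence and tumor that never grows during 2 to 4 years of follow-up. Growth is measured from the smallest diameter, so residual tumor that regrows does become an event, and the figures are then much lower. This also stands.
- **Counting persistence in the trial alone could bias the test against the treatment.** This is correct if the 65% is recurrence-based, and the fix has to deal with it.

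**Conclusion.** The gap is real and should be closed. The primary event is undefined in section 8, and the only rule the plan supplies scores persistent, non-growing cervical tumor as local control. The 4.8 points per patient is plain arithmetic, relative to a definition that counts persistence as failure.

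The effect on the test is conditional. It needs the 65% to have counted persistence as failure, which is not stated, and it depends on an assumed persistence share of 5-15% and on how residual tumor behaves. On those assumptions the false-success rate of about 4% becomes 6-13% (median 1 further year to progression), 7-22% (median 2 years), or at worst 11-52% (no growth at all). What can be said without assumptions is narrower: nothing shows that the 65%, the 85% and the trial's own endpoint use one definition, and a one-sample test depends on that.

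**What to change.** - In sections 7.1.6 and 8.3.1, define local failure as recurrent or persistent cervical tumor. Judge persistence at the 6-month visit by the examination already scheduled and any available imaging, confirm it at the next visit, and state the date the event takes.
- State how patients who die or are lost between the 6-month visit and confirmation are handled.
- Confirm that the 65% and the 85% use this definition, or restate them so that they do. Without this step the change could bias the test the other way. If both are restated on the same definition at unchanged values, n stays at 21.
- Report the Kaplan-Meier estimate and the one-sample log-rank test under both the persistence-as-failure and the growth-only definitions.

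**Cost.** This is mainly a wording change that uses visits already in section 6.3. Axial imaging is required only once within 14 months (section 6.3.1), so the 6-month judgement will often rest on examination alone, and some benign residual change may be counted as failure. The estimate and the power may be less favourable, and materially so if 85% is a progression-only rate.
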